#### 2.1.1.4 Day of last dose of randomized study treatment

The date of last dose will be collected via the CRF.

The participant's exposure will be calculated considering the last dose + 84 days or last visit whichever occurs earlier.

For safety analysis, on-treatment is defined as assessments within last dose + 84 days.

#### 2.2 Analysis sets

The following analysis sets will be used in this study:

The Randomized Analysis Set (RAS) consists of all randomized participants.

The Full Analysis Set (FAS) comprises all participants in the RAS, excluding mis-randomized patients.

Mis-randomized participants are defined as cases where IRT contacts were made by the Investigator/qualified site staff either prematurely or inappropriately to confirmation of the patient's final randomization eligibility and treatment was not administered to the patient.

According to the intent-to-treat principle, participants will be analyzed according to the treatment they have been assigned to at randomization. If the actual randomization stratum is different to the assigned stratum in IRT, the actual stratum will be used in analyses.

The **Safety Set (SAF)** includes all participants who received at least one dose of study treatment. Participants will be analyzed according to the study treatment received, where treatment received is defined as the randomized/assigned study treatment if the participant took at least one dose of that treatment or the first treatment received if the randomized/assigned study treatment was never received.

#### 2.2.1 Subgroup of interest

Due to the early termination of the study, subgroup analysis will not be performed.

# 2.3 Patient disposition, demographics and other baseline characteristics

## 2.3.1 Patient disposition

The number of participants screened will be presented. In addition, the reasons for screen failures will be provided.

The number and percentage of participants in the RAS who completed the study periods, and who discontinued the study prematurely (including the reason for discontinuation) will be presented by study period for each treatment group and all participants. A listing will also be provided with detailed reasons for treatment discontinuation.

For each protocol deviation (PD), the number and percentage of participants for whom the PD applies will be tabulated.

#### 2.3.2 Demographics and other baseline characteristics

The following common background and demographic variables will be summarized:

#### **Continuous variables:**

- Age
- Height
- Weight
- Body mass index (BMI) = (body weight in kilograms) / (height in meters)

For BMI, height and body weight, the last value prior to randomization is used. If there is no weight or height recorded prior to administration of the study drug, BMI will be missing.

#### **Categorical variables:**

- Sex
- Race

#### Ethnicity

Baseline disease characteristics will also be summarized for the following variables:

Time since first diagnosis of RCT (weeks), time since symptoms started (weeks), tear status (no tear/partial tear), WORC total score, WORC PSD score,
 PROMIS SF UE score,
 affected arm (Dominant arm/Non-dominant arm), pain medication during screening (No/Yes).

Time since diagnosis of RCT (weeks) will be calculated using the following formula:

Time since diagnosis = (inform consent date – first diagnosis date + 1)/7

Time since current symptoms of RCT (weeks) will be calculated using the following formula:

Time since current symptoms = (inform consent date – current symptoms date + 1)/7

The first diagnosis date of RCT will be imputed according to the imputation rules in Section 5.1.4.

Unless otherwise specified, summary statistics will be presented for continuous variables for each treatment group and for all participants (total) in the RAS. The number and percentage of participants in each category will be presented for categorical variables for each treatment group and all participants (total) in the RAS.

#### 2.3.3 Medical history

Any condition entered on the *Relevant medical history / current medical conditions* CRF will be coded using the Medical dictionary for regulatory activities (MedDRA) dictionary. They will be summarized by treatment group, system organ class (SOC) and preferred term (PT) of the MedDRA dictionary.

Summaries for RCT specific medical history will be provided for the following parameters:

- Time since first diagnosis of RCT (weeks)
- Total number of prior episodes of tendinopathy
- Prior affected shoulder (left/right/bilateral)
- Time since current symptoms of tendinopathy started (weeks)
- Current affected shoulder (left/right)
- Dominant shoulder (left/right)

# 2.4 Treatments (study treatment, rescue medication, concomitant therapies, compliance)

#### 2.4.1 Study treatment / compliance

The analysis of study treatment data will be based on the SAF.

The duration of exposure to study treatment will be summarized by treatment group. In addition, the number and percentage of participants with cumulative exposure levels (e.g., any exposure,  $\geq 1$  week,  $\geq 2$  week,  $\geq 3$  week,  $\geq 4$  weeks,  $\geq 8$  weeks, etc.) will be presented.

Duration of exposure will be defined as the time from first dose of study treatment to the end of study period. The end of study period will be defined as the last dose + 84 days or last visit whichever occurs earlier. For participants who discontinued and have their last visit earlier than last dose + 84 days, the end of study exposure will be the date of the last study visit in the follow-up period or in the corresponding treatment period.

Duration of exposure (days) = min (last visit date, last dose date + 84 days) - first dose date + 1

Duration of exposure (years) = duration of exposure (days) / 365.25

Duration of exposure (100 subject years) = duration of exposure (years) / 100

The analyses of duration of exposure described above will be done for the entire study treatment period.

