Participants who **disagree to continue attending all remaining study** visits after prematurely discontinuing the study treatment (including those who initially continued to attend site visits but subsequently decided to discontinue the study) should perform an end of treatment visit, 4 weeks after their last study treatment administration (or as soon as possible upon the decision of study discontinuation if more than 4 weeks elapsed since last dose of study treatment). A corresponding end of study post-treatment safety follow up visit should be performed 12 weeks after the last administration of the study treatment (or as soon as possible, if more than 12 weeks elapsed since last dose of study treatment).

If the participant cannot or is unwilling to attend any visit(s), the site staff should maintain regular telephone contact with the participant, or with a person pre-designated by the participant. This telephone contact should preferably be done according to the study visit schedule.

After discontinuation from study treatment, at a minimum, in abbreviated visits, the following data should be collected at clinic visits or via telephone/email contact:

- New / concomitant treatments
- AEs / Serious Adverse Events

The Investigator must also contact the IRT to register the participant's discontinuation from study treatment.

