9.4.2 Safety endpoints

For all safety analyses, the safety set will be used. All listings and tables will be presented by treatment group.

Safety summaries (tables, figures) include only data from the on-treatment period with the exception of BSL data which will also be summarized where appropriate (e.g., change from BSL summaries). In addition, a separate summary for death including on treatment and post treatment deaths will be provided. In particular, summary tables for adverse events (AEs) will summarize only on-treatment events, with a start date during the on-treatment period (treatment-emergent AEs).

The on-treatment period lasts from the date of first administration of study treatment to 84 days after the date of the last actual administration of any study treatment.

Adverse events

All information obtained on AEs will be displayed by treatment group and participant.

The number (and percentage) of participants with treatment-emergent AEs (i.e., events started after the first dose of study treatment or events present prior to the first dose of study treatment but increased in severity based on preferred term and on or before last dose + 84 days) will be summarized in the following ways:

- by treatment, primary system organ class and preferred term.
- by treatment, primary system organ class, preferred term and maximum severity.
- by treatment, Standardized MedDRA Query (SMQ) and preferred term.

Separate summaries will be provided for study medication related AEs, death, serious AEs, other significant AEs leading to discontinuation, and AEs leading to dose adjustment.

The number (and proportion) of participants with AEs of special interest/related to identified and potential risks will be summarized by treatment.

If a participant reported more than one AE with the same preferred term, the AE with the greatest severity will be presented. If a participant reported more than one AE within the same primary system organ class, the participant will be counted only once with the greatest severity at the system organ class level, where applicable. Serious AEs will also be summarized.

As appropriate, the incidence of AEs will be presented per 100 subject years of exposure (exposure-adjusted incidence rates).

Separate summaries will be provided for death, serious AE, other significant AEs leading to discontinuation and AEs leading to dose adjustment (including study treatment discontinuation).

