#### 2.7.1 Adverse events (AEs)

All information obtained on adverse events will be displayed by treatment group and participant.

The number (and percentage) of participants with treatment emergent adverse events will be summarized in the following ways:

- by treatment, primary system organ class and preferred term.
- by treatment, primary system organ class, preferred term and maximum severity.

Confidence intervals for the crude rate will be derived as described in Section 5.4.

Treatment emergent adverse events are defined as events started on or after the first dose of study medication or events present prior to the first dose of study medication but increased in severity on or after dosing based on preferred term and within last dose + 84 days (inclusive).

A participant with multiple adverse events within a primary system organ class is only counted once towards the total of the primary system organ class.

Separate summaries will be provided for study treatment related adverse events, death, serious adverse event, other significant adverse events leading to discontinuation and adverse events leading to dose adjustment or interruption.

Adverse events reported will be presented in descending frequency according to its incidence in the AIN457 300 mg group starting from the most common event. AEs will be summarized by presenting the number and percentage of participants having any AE, having an AE in each primary system organ class and having each individual AE (preferred term).

Summaries will also be presented for AEs by severity and for study treatment related AEs. If a particular AE 'severity' is missing, this variable will be listed as missing and treated as missing in summaries. If a participant reported more than one adverse event with the same preferred term, the adverse event with the greatest severity will be presented. If a participant reported more than one adverse event within the same primary system organ class, the participant will be counted only once with the greatest severity at the system organ class level, where applicable. Of note, AEs by severity will be provided by SOC in the study report and AEs by severity and PTs may be provided if required at ad-hoc basis.

The MedDRA version (version 27.0 or above) used for reporting the study will be described in a footnote.

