#### 5.4.3 Exposure adjusted incidence rate and related risk estimates

#### 5.4.3.1 Exposure adjusted incidence rate and $100*(1-\alpha)\%$ confidence interval

It will be assumed that for each of n participants in a clinical trial the time  $t_j$  (j=1,...,n) to the first occurrence of a certain event is observed, or if the event was not experienced, the (censored) time to the end of the observation period. The sequence of first occurrences of an event will be

modeled to follow approximately a Poisson process with constant intensity  $\theta$ . The rate

parameter 
$$\theta$$
 will be estimated as  $\lambda = D/T$ , where  $T = \sum_{j=1}^{n} t_j$  and  $D$  is the number of participants

with at least one event. Conditionally on T, an exact  $100*(1-\alpha)\%$  confidence interval for a Poisson variable with parameter  $\theta T$  and observed value D can be obtained based on (Garwood 1936), from which an exact  $100*(1-\alpha)\%$  confidence interval for D/T will be derived as follows (Sahai 1993):

Lower confidence limit  $L = \frac{0.5c_{\alpha/2,2D}}{T}$  for D > 0, 0 otherwise,

Upper confidence limit 
$$U = \frac{0.5c_{1-\alpha/2,2D+2}}{T}$$

Where  $c_{\alpha,k}$  is the  $\alpha$ th quantile of the Chi-square distribution with k degrees of freedom.

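### Exposure-adjusted AE rates count events up to 84 days after the last dose, but event-free time appears to stop at the last visit, so rates run slightly high where leavers are followed by telephone

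*SAP*

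**What the plan says.** **Events.** SAP 2.7 runs the on-treatment period from first dose to 84 days after the last. SAP 2.7.1 counts an AE as treatment-emergent if it falls "within last dose + 84 days (inclusive"). Only events before first dose or beyond those 84 days are flagged as not treatment-emergent. The last visit plays no part.

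**Time.** SAP 2.4.1 states: "The end of study period will be defined as the last dose + 84 days or last visit whichever occurs earlier". The formula is "Duration of exposure (days) = min (last visit date, last dose date + 84 days) - first dose date + 1". For participants who leave early, "the end of study exposure will be the date of the last study visit in the follow-up period or in the corresponding treatment period". SAP 2.1.1.4 gives the same minimum.

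**Rate.** SAP 5.4.3.1 estimates the rate as D/T. D is the number of participants with at least one event and T is the sum of individual times. A participant with the event contributes time to its first occurrence. A participant without it contributes "the (censored) time to the end of the observation period", a term the SAP neither defines nor links to 2.4.1. SAP 2.7.1 plans these rates with 95% intervals for AEs, SAEs and RMP risks. Protocol 9.4.2 says that, as appropriate, "the incidence of AEs will be presented per 100 subject years of exposure (exposure-adjusted incidence rates").

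**Follow-up after visits stop.** Protocol 7.1 asks those who stop attending for visits 4 and 12 weeks after the last dose. It adds: "If the participant cannot or is unwilling to attend any visit(s), the site staff should maintain regular telephone contact with the participant". AEs and SAEs are in the minimum data to be collected at a clinic or by telephone or email. Protocol 4.7 adds a safety call 60 days after the last dose for those who do not return. Protocol 8.6.1 continues AE monitoring for at least 12 weeks after the last dose.

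**The concern.** A person-time rate is unbiased only if events and time at risk are observed over the same interval. Here the event interval can outlast the time interval by up to 84 days, and the protocol arranges for AEs to be collected in that gap. A participant who reports an AE by telephone raises the event count. A participant telephoned over the same weeks who reports nothing has those weeks left out. The error always raises the rate, and it differs between arms if more participants stop attending in one arm than in the other. What is at stake is the set of exposure-adjusted rates and their Poisson intervals; crude incidence is not touched.

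**Working it through.** The documents state no exposure-adjusted rate, so there is no figure of the plan's own to reproduce. The check has three steps.

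**1. Who is affected.** The gap is (last dose + 84 days) minus the last visit, when positive.
- Completers: last dose Day 85; 85 + 84 = 169, the Week 24 visit. Gap 0.
- Leavers who attend the visit 12 weeks after the last dose: 84 − 84 = 0.
- Leavers who attend only the 4-week visit: 84 − 28 = 56 days.
- Leavers with no visit after the last dose: 84 days.

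**2. A small worked case under 5.4.3.1.** Take one arm of 10 (assumed): 8 event-free completers and 2 leavers with last dose Day 29 and last visit Day 57. One leaver reports an AE by telephone on Day 100; the other is telephoned to Day 113 and reports nothing.
- As written: T = 8×169 + 100 + 57 = 1509 days; rate = 1/1509 × 36,525 = 24.2 per 100 subject-years.
- Events and time both to Day 113: T = 8×169 + 100 + 113 = 1565 days; rate = 23.3.
- Ratio 1565/1509 = 1.037. The 56 lost days all belong to the event-free leaver.

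**3. Expected bias.** Assume a constant daily hazard h. A fraction f of the arm has last dose on Day 29, last visit on Day V and telephone follow-up to Day W = 29 + 84 = 113; the rest complete 169 days. Per participant:
- D = (1 − f)(1 − e^(−169h)) + f(1 − e^(−113h))
- T with matched end dates = D/h
- T as written = D/h − f(W − V)e^(−113h)

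The subtracted term is the telephone time of leavers who never have the event. With matched end dates D/T equals h exactly.

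*Common event.* Protocol 2.3 reports 70 of 96 proof-of-concept participants with any AE. Taken as a constant hazard over 169 days (an assumption), h = −ln(26/96)/169 = 1.3063/169 = 0.00773 per day, or 282.3 per 100 subject-years. For f = 0.1 and V = 57:
- D = 0.9×0.7292 + 0.1×0.5825 = 0.7145, so D/h = 92.4 days
- time lost = 0.1×56×0.4175 = 2.34 days
- ratio = 92.4/(92.4 − 2.34) = 1.026

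*Rare event.* Assume 20 per 100 subject-years.

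| Event | Last visit | f = 10% | f = 20% |
|---|---|---|---|
| Common | Day 57 | +2.6% | +5.4% |
| Common | Day 29 | +3.9% | +8.4% |
| Rare | Day 57 | +3.5% | +7.5% |
| Rare | Day 29 | +5.3% | +11.7% |

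The relative error is larger for rare events because nearly every leaver is then event-free and loses the whole gap.

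**The case against.** A reader might infer that telephone-followed participants add events without adding any time. The documents do not support that. SAP 5.4.3.1 does not divide by the total duration of exposure in 2.4.1: a participant whose first AE falls on Day 100 contributes time to Day 100. Capping everyone's time at the last visit would give larger errors for the common event (+3.3% and +6.9% with last visit Day 57, +5.6% and +12.2% with Day 29, for f = 10% and 20%), but that is not the planned estimator.

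Three further objections have force.
- The problem needs two readings that the SAP does not state: that the observation period in 5.4.3.1 ends at the 2.4.1 minimum, and that a telephone contact is not a visit. Protocol 7.1 speaks of abbreviated visits whose data may come by telephone or email. If these count as visits, most of the gap closes.
- Protocol 7.1 asks leavers for a 12-week safety visit, and those who attend it have no gap. Only those who miss it matter, and the documents give no number.
- The rates are descriptive and imprecise. With 7 events (assumed), the exact Poisson interval runs from about 0.4 to 2.1 times the estimate, which dwarfs a shift of a few per cent. Crude incidence is reported alongside.

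These points limit the size of the problem. They do not reconcile the two end dates, and the undefined terms are part of the defect.

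**Conclusion.** The mismatch stands, as a minor point. Events are counted to last dose plus 84 days; on the natural reading of 5.4.3.1, event-free time stops at the earlier of that date and the last visit. For leavers followed only by telephone, the exposure-adjusted rates are therefore biased upward. Under the 5.4.3.1 rule the bias is about 3% to 8% for a common event and 4% to 12% for a rare one, if 10% to 20% of an arm are such leavers. This rests on an assumed constant hazard, last dose on Day 29, no attendance at the 12-week visit, telephone follow-up for the full 84 days, and telephone contacts not counting as visits.

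A difference in bias between arms would need different attrition, of which the documents give no evidence. Nor can the effect be fixed by assuming 21 participants: SAP 1 gives 21 as the number randomized at termination and lets those screened by 7 May 2024 continue, and results are presented by arm.

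**What to change.** In SAP 5.4.3.1, define the end of the observation period and use it for both events and time at risk in the exposure-adjusted rates: the earlier of last contact of any kind, telephone included, and last dose plus 84 days. State in 2.4.1 whether a telephone contact counts as a visit.

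If last-contact dates are not in the database, cap both events and time at the last visit for these rates only, and leave crude incidence on the full 84-day window. Under a constant hazard this also removes the bias.

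Apply the same date in the AE end-date imputation in 5.1.2, which now uses the last-visit minimum. As it stands, a telephoned AE that begins after the last visit and has a partial end date would be given an end before its own onset; if its start date is also imputed, that start is then moved back to the imputed end.

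The cost is a few lines of SAP text and one derivation. It may also mean retrieving contact dates from site records, because Protocol 4.7 keeps the 60-day call in source documentation.

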#### 2.4.1.1 Analysis visit window

Analysis visit windows will be used for the data that is summarized by visit; they are based on the study visit and evaluation schedule and comprise a set of days around the nominal visit day. For any assessment, there are protocol defined scheduled visits around which analysis visit windows were created to cover the complete range of days within the study. Visit windows will vary depending on the frequency of the analysis visit. The analysis visit windows are defined in Table 2-1. In the tables, the days are counted since the first dose of the study treatment (i.e., Study Day 1).

When visit windows are used, all visits will be re-aligned, i.e., they will be mapped into one of the visit windows. E.g., if the *Week 4* visit of a participant is delayed and occurs on Day 46 instead of on Day 29, it will be re-aligned to visit window *Week 8*. In the case of major deviations from the visit schedule, or due to unscheduled visits, several assessments of a participant may fall in a particular visit window (either scheduled or unscheduled). Statistical approaches to handle multiple assessments in a given visit window are specified below.

In general, if two consecutive visits  $V_t$  and  $V_s$  are x days apart (t < s), when x is even, the upper limit for  $V_t$  will be  $V_t + x/2$  and the lower limit for  $V_s$  will be ( $V_s - x/2$ ) + 1; when x is odd, x/2 is rounded down to integer y, then the upper limit of the visit window for  $V_t$  will be  $V_t + y$  and the lower limit for the visit  $V_s$  will be  $V_s - y$ . The algorithm needs to ensure that visit windows are not overlapping and there are no gaps, such that each assessment can be uniquely allocated to one visit window, e.g., if Week 8 visit is scheduled at day 57, Week 12 visit is scheduled at day 85 and Week 16 visit is scheduled at day 113, then the visit window for week 12 extends from Day 72 to Day 99.

Of note, participants are allowed to have gaps in visits.

Table 2-1 Analysis visit windows

Analysis Visit	Target Day	Analysis Visit Window	Group 1	Group 2	Group 3	Group 4	Group 5	Group 6	Group 7
Baseline	1*	≤ 1	≤ 1				≤ 1	≤ 1	≤ 1
Week 1	8	2-11							
Week 2	15	12-18	2-22						2-22

Analysis Visit	Target Day	Analysis Visit Window	Group 1	Group 2	Group 3	Group 4	Group 5	Group 6	Group 7
Week 3	22	19-25							
Week 4	29	26-43	23-43				2-71		23-43
Week 8	57	44-71	44-71						44-71
Week 12	85	72-99	72-99						72-99
Week 16	113	100-127	100-127				72-183	2-183	100-141
Week 20	141	128-155	128-155						
Week 24	169	156-183	156-183						142-183
Group 1: W	Group 1: WORC Total, PROMIS SF UE, WORC PSD,								
Group 2: Group 3: Group 4:									

